Baseline characteristics of the patients will be described as mean and standard deviation among continuous variables while percentage will be utilized for categorical data. In comparing the two groups, t-test will be used to compare means such as BBPSscore, while chi square test will be utilized for categorical variables such as proportion of adequate bowel preparation. All significant test will be done at 5 % level. A non inferiority margin of 0.05 was set. Medcalc statistical calculator will be utilized to carry out statistical computations.

Results

Patients Demographics

A total of 75 patientseach from low residue diet and clear liquid diet group were included in this study whose average age is 67.9 and 64.9 respectively (p=.0515). (Table 1). It also showed that around 82.7% of the patients in low residue are elderly, which is not significantly different from the resulting proportion of elderly patients in clear liquid diet group (72%). (Table 1) Moreover, both group is composed mostly of male (61% vs 75%, Low Residue vs Clear liquid), while proportion of occurrence of diabetes mellitus, chronic kidney disease and chronic liver disease is also not significantly different for the two groups.(Table 1). There were also no differences in terms of cecal intubation rate, withdrawal time, out patients and in patient's number.(Table 1).

Table 1. Patient Baseline Demographic Information

Profile	Low Residue Diet (n=75)	Clear Liquid Diet (n=75)	p value
Age (years), mean±sd	67.9 ± 9.5	64.9 ± 9.0	0.0515 ^{ns}
Elderly (>60), n,%	62 (82.7)	54 (72.0)	0.1200 ^{ns}
Sex, n,%			
Male	46 (61.3)	56 (74.7)	0.0811 ns

Female	29 (38.7)	19 (25.3)	
Comorbidities, n,%			
Diabetes Mellitus	32 (42.7)	29 (38.7)	0.6192 ns
Chronic Kidney Disease	11 (14.7)	6 (8.0)	0.1993 ns
Chronic Liver Disease	5 (6.7)	5 (6.7)	1.0000 ns
Others			
Cecal intubation rate	75 (100)	75(100)	1.0
Withrawal time	8.6±2.2	8.95±2.5	0.3642
In patients	44(58.7)	39(52)	0.4131
Out patients	31(41.3)	36(48)	

Adequacy of Bowel Preparation

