The proportion of patients who developed nausea and vomiting were not statistically significant between the two groups(5.35 vs 12 %,p=0.148)(Table 3a). However, the occurrence of abdominal pain/cramping/discomfort (34.7%) and bloatedness (44%) are significantly higher in clear liquid diet group compared to low residue diet group(16% and 26.7% respectively, p=0.0088 and0.0269) (Table 3a). Moreover, patients in the LRD group were less hungry before colonoscopy as compared to CLD group(4.16 vs 3.72, p=0.0027). Patient's satisfaction with the diet showed a higher proportion of patients in the LRD group rated the procedure easy(12%) and fair (78.7 %) compared to CLD group (3% and 72% respectively, p=0.0178). Likewise, in terms of willingness to repeat the procedure, patients who said yes is significantly higher for low residue diet group (93%) as compared to only 81.3% for Clear liquid diet group. On the other hand, among patients with Diabetes Mellitus, Chronic

Kidney Disease, and Chronic liver disease showed no significant difference between the two groups in terms of symptoms, hunger score, satisfaction with diet and willingness to repeat procedure.(Table 3b-3d).

Table 3e showed that among elderly patients, proportion of patients with abdominal pain(37%) was higher for Clear liquid diet group compared to LRD group (12%, p=0.0343). Finally, in terms of willingness to repeat the procedure, elderly patients who said yes is significantly higher for low residue diet group (93.5%) as compared to only (81.5%) for Clear liquid diet group.

Table 3a Patients Tolerability (Gastrointestinal Symptoms)

	Low Residue Diet (n=75)	Clear Liquid Diet (n=75)	p value
GI Symptoms			
Nausea/Vomiting,n,%	4 (5.3)	9 (12.0)	0.1481 ^{ns}
Abdominal Pain/Cramping/Discomfort, n, %	12 (16.0)	26 (34.7)	0.0088*
Bloatedness,n,%	20 (26.7)	33 (44.0)	0.0269*
Hunger Score, mean±sd	4.16 ± 0.81	3.72 ± 0.95	0.0027*
Satisfaction with Diet, n, %			
Easy	9 (12.0)	3 (4.0)	
Fair	59 (78.7)	54 (72.0)	0.0178*
Difficult	7 (9.3)	18 (24.0)	
Willingness to Repeat Procedure, n, %			
Yes	70 (93.3)	61 (81.3)	0.0277*
No	5 (6.7)	14 (18.7)	0.0277*

Table 3b Patients Tolerability (Gastrointestinal Symptoms) for DM

	Low Residue Diet (n=32)	Clear Liquid Diet (n=29)	p value
--	----------------------------	-----------------------------	---------

GI Symptoms			
Nausea/Vomiting,n,%	2 (6.2)	5 (17.2)	0.1822 ns
Abdominal Pain/Cramping/Discomfort, n, %	7 (21.9)	12 (41.4)	0.1033 ns

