5=Comfortable, neither hungry nor full	19 (25.3)	5 (6.7)
6=comfortably full	4 (5.3)	3 (4.0)
7=Very full, feel as if you have overeaten	0 (0.0)	2 (2.7)
8=Uncomfortably full	0 (0.0)	0 (0.0)
9=Very uncomfortably full, needed to loosen you belt	0 (0.0)	0 (0.0)
10 Stuffed to the point of feeling sick,in a food coma	0 (0.0)	0 (0.0)

Table 5. Patient Satisfaction

Satisfaction	Low Residue Diet (n=75)	Clear Liquid Diet (n=75)	p value
How easy or difficult was it to consume the diet regimen			
Easy	9 (12.0)	3 (4.0)	
Fair	59 (78.7)	54 (72.0)	0.0178*
Difficult	7 (9.3)	18 (24.0)	
Were you able to consume the entire preparation as instructed			
Yes	73 (97.3)	71 (94.7)	0.4062ns
No	2 (2.7)	4 (5.3)	0.4062 ^{ns}
Please describe your overall experience of the study preparation			
Easy	9 (12.0)	3 (4.0)	
Fair	59 (78.7)	54 (72.0)	0.0178*
Difficult	7 (9.3)	18 (24.0)	
Would you ask your doctor for this preparation again if you needed another colonoscopy in the future			
Yes	70 (93.3)	61 (81.3)	0.0277*
No	5 (6.7)	14 (18.7)	
Would you refuse the same preparation again if it were to be prescribed to you in the future			
Yes	5 (6.7)	14 (18.7)	0.0277*
No	70 (93.3)	61 (81.3)	0.0277*

Discussion

The adequacy of bowel preparation is an important quality measure for optimal colonoscopy. The efficacy of bowel preparation is vital to guarantee the accuracy and proper visualization of colonoscopy test and treatment. Conventionally, the clear liquid dietary regime

was commonly selected to perform the bowel preparation; however, apparentrestrictions such as patients tolerability and satisfaction limits this approach.

In this study, we examined the effect of low residue diet onthe adequacy of bowel preparation using the BBPS compared to clear liquid diet. It showed that low residue diet is non-inferior to clear liquid diet in the efficacy of bowel preparation. Our findings suggested that LRD did not compromise the adequacy of bowel preparation relative to CLD. This is consistent with the results of most studies.

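### Diet satisfaction (Easy/Fair/Difficult) is ordered but is tested by a 2-df chi-square that ignores the order: valid, but about 7 to 9 points of power lower than a rank test at the observed proportions

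*Protocol*

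**What the plan says.** The Statistical Analysis section names two methods for comparing groups: a t-test for means and, for everything categorical, chi-square: "chi square test will be utilized for categorical variables such as proportion of adequate bowel preparation". It adds "All significant test will be done at 5 % level". No rank, trend or ordinal method appears.

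The Outcomes section plans a questionnaire before colonoscopy that covers tolerability, hunger and satisfaction with the diet. Table 5 gives the item, "How easy or difficult was it to consume the diet regimen", with the answers Easy, Fair and Difficult. Tables 3a to 3e report satisfaction overall and by subgroup. The Results text reads the whole-trial comparison in a direction, saying that more low residue patients "rated the procedure easy(12%) and fair (78.7 %) compared to CLD group (3% and 72% respectively, p=0.0178". The Discussion concludes that satisfaction was better on the low residue diet.

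**The concern.** Easy, Fair and Difficult have a natural order, and the question asked of them is directional: is the low residue diet easier to follow? A Pearson chi-square on a 2×3 table treats the levels as unlabelled categories. It spends two degrees of freedom on any difference in distribution, including patterns that have no direction. A rank test uses the order and puts its single degree of freedom on a shift towards easier or harder.

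At stake is efficiency, not validity. Satisfaction belongs to the patient-experience side of the trial, and the specific objective is tolerability in special populations, where the groups are smaller than the full sample. The chi-square p also gives no size or direction of effect, although the text draws a directional conclusion from it.

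**Working it through.** **Inputs.** Satisfaction counts as Easy/Fair/Difficult, low residue vs clear liquid, from Tables 3a, 3b, 3c and 3e. (The Results text gives 3% Easy on clear liquid; Table 3a gives 3 patients, and 3/75 = 4.0%. The table counts are used.) Two-sided 5% level.

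**Step 1: reproduce the printed p.** Whole trial, 9/59/7 vs 3/54/18. With 75 per arm, the expected counts in each arm are 6, 56.5 and 12.5.

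χ² = Σ(O−E)²/E = 2 × (3²/6 + 2.5²/56.5 + 5.5²/12.5) = 2 × (1.500 + 0.111 + 2.420) = 8.06. On 2 df, p = exp(−8.06/2) = 0.0178, as printed.

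**Step 2: keep the order (Wilcoxon with midranks).** The midranks are 6.5 (12 Easy), 69 (113 Fair) and 138 (25 Difficult).

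- Rank sum, low residue: 9×6.5 + 59×69 + 7×138 = 5095.5.
- Expected: 75×151/2 = 5662.5.
- Tie-corrected variance: n₁n₂/12 × [(N+1) − Σ(t³−t)/(N(N−1))] = 40158.
- z = −567/200.4 = −2.83, p = 0.0047.

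Elderly, 6/50/6 vs 3/38/13: midranks 5, 53.5 and 107; rank sum 3347 against 62×117/2 = 3627; variance 18234; z = −280/135.0 = −2.07, p = 0.038.

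| Group | Counts | Printed p | 2-df χ² (p) | Wilcoxon p |
|---|---|---|---|---|
| Whole trial | 9/59/7 vs 3/54/18 | 0.0178 | 8.06 (0.0178) | 0.0047 |
| Diabetes | 6/22/4 vs 2/20/7 | 0.2500 | 2.77 (0.2500) | 0.103 |
| Chronic kidney disease | 1/10/0 vs 1/4/1 | 0.3167 | 2.30 (0.3167) | 0.71 |
| Elderly | 6/50/6 vs 3/38/13 | 0.0845 | 4.69 (0.096) | 0.038 |

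The proportional-odds common odds ratio in favour of low residue is 3.1 (95% CI 1.4 to 7.0) overall and 2.5 (1.04 to 6.2) in the elderly.

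**Step 3: how firm is the elderly value?** Other ordinal analyses of the same counts give: proportional odds, likelihood ratio 0.035 and Wald 0.040; asymptotic trend 0.041; exact Wilcoxon 0.043; exact trend with equally spaced scores 0.054. Moving one patient by one category towards no difference, in each of the four possible ways, gives Wilcoxon p-values of 0.051, 0.059, 0.063 and 0.065.

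**Step 4: power (100,000 simulated trials per scenario).**

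| Scenario | Chi-square | Wilcoxon | Loss |
|---|---|---|---|
| Observed proportions, 75 vs 75 | 73.9% | 83.0% | 9.1 points |
| Observed proportions, elderly 62 vs 54 | 48.4% | 55.5% | 7.1 points |
| Observed proportions, diabetes 32 vs 29 | 28.9% | 37.4% | 8.6 points |

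The protocol plans no effect size for satisfaction, so proportional-odds shifts of 1.5 to 4 from the clear-liquid distribution were assumed as well. The loss was then 4.6 to 11.4 points at 75 per arm and 4.3 to 11.2 points at 62 vs 54. In separate null simulations both tests had a type I error of about 5%.

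**Step 5: the hunger categories.** Table 4 (levels 3 to 7: 15/37/19/4/0 vs 38/27/5/3/2) gives a 4-df Pearson p of 0.0002, as printed. The same order-ignoring test was used there.

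**Step 6: the elderly entry.** The printed 0.0845 is not the chi-square p of the printed satisfaction counts. It equals the bloatedness p in the same table. For bloatedness (19/62 vs 25/54) the chi-square is 3.003; multiplied by (N−1)/N = 115/116 it is 2.977, p = 0.0845. The same form gives 0.0269 for whole-trial bloatedness, also as printed, but 0.098 for elderly satisfaction. The value therefore belongs to bloatedness.

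**Step 7: chronic liver disease.** Table 3d prints 0/3/0 for five clear-liquid patients, so two are unaccounted for. The printed p of 0.4444 is Fisher's exact test if both answered Difficult: 2 × 56/252 = 0.4444. The printed counts cannot confirm that.

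**The case against.** The strongest reply is that nothing invalid was done. Chi-square holds its 5% level, satisfaction is one item of a secondary questionnaire, and the whole-trial result is significant either way. All of that stands, and it limits the point to efficiency and to matching the test to the scale.

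A reader might infer that the wrong test hid a real benefit in the elderly. The documents do not support that. The ordinal p-values straddle 0.05 (0.035 to 0.054), one patient moved by one category takes the Wilcoxon p above 0.05, and this is one of many unadjusted subgroup tests. The printed 0.0845 is a copying slip, so it says nothing about the choice of test.

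A reader might also infer that the loss is worst in the smallest groups. The figures say otherwise: at the observed proportions it is largest in the full sample (9.1 points). In chronic kidney disease (17 patients, not a monotone pattern) the rank test gives the larger p, 0.71 against 0.32.

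Three further replies stand in part. Power at observed proportions is post-hoc and adds little to the p-values, hence the range over assumed shifts. For hunger, Table 3a already compares mean scores (p = 0.0027), which uses the order, so only the category comparison in Table 4 is affected. Changing a test once results are known is post-hoc selection, so the existing p-values should stay visible.

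Two replies do not remove the point. The quoted sentence does not name satisfaction, but the printed p-values show that the rule was applied to it. A separate analysis plan might have refined the method, but this document states its test and reports the results.

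**Conclusion.** The point holds as one of efficiency. An ordered secondary outcome was tested without its order. At the observed proportions this costs about 9 points of power overall and about 7 in the elderly, and roughly 4 to 11 points under the assumed proportional-odds shifts. Conclusions do not change for the whole trial (0.0178 to 0.0047), diabetes (0.250 to 0.103) or chronic kidney disease (0.32 to 0.71). The elderly comparison moves from 0.096 to about 0.04 and should be described as borderline.

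Two reporting errors stand whichever test is preferred: the elderly satisfaction p in Table 3e, and the incomplete clear-liquid satisfaction column in Table 3d. All of this assumes that the other printed satisfaction counts are correct.

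**What to change.** - **Statistical Analysis:** limit chi-square to binary or unordered variables. State that ordered items (satisfaction in Tables 3a to 3e and 5; the category comparison of the hunger scale in Table 4) are compared by the Wilcoxon rank-sum test, exact in small subgroups, with a common odds ratio and 95% CI where estimable.
- **Tables:** because results are known, print the ordinal result beside the chi-square p and label it a post-hoc revision. Do not describe the elderly result as a reversal.
- **Table 3e:** replace the elderly satisfaction p of 0.0845 with 0.096, the chi-square p of the printed counts.
- **Table 3d:** reconcile the clear-liquid satisfaction column with source data before re-analysing it.

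The cost is a short addition to the analysis section and a re-run on counts already printed. Table 3d is the exception, because it needs the source records. There is one small statistical downside: a rank test is less sensitive when a diet moves patients from both ends towards the middle, as the small kidney-disease subgroup happens to show (10 of 11 Fair against 4 of 6).

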[figure not shown]
All patients will be instructed to ingest the standard operating procedure (SOP) bowel cleansing agent of VMMC. Patients whose colonoscopy was scheduled at 8 AM will be instructed to take lactulose 60cc followed by 4-5 glasses of water at 1pm, 3pm and 5pm the day before the procedure. They will also be instructed to take bisacodyl 5mg/tab, 2 tablets followed by 4-5 glasses of water at 7pm. Those patients schedule after 8am will follow the same regimen. They will be instructed to take the lactulose and bisacodyl 15 hours and 12 hours respectively prior to colonoscopy.

[figure not shown]
Outcomes

[figure not shown]
The primary outcome is the efficacy or adequacy of bowel preparation. It will be measured by the Boston Bowel Preparation Scale (BBPS), which is a validated and reliable scale. Secondary outcomes such as patient's tolerability of the regimen will be assessed by inquiring on the occurrence of gastrointestinal symptoms related to the dietary regimen, i.e, nausea, vomiting, bloatedness, abdominal cramps/discomfort. Other outcomes such as cecal intubation rate, polyp detection rate and insertion/withdrawal time will also be measured.

The efficacy of bowel preparation will be assessed by three gastroenterology consultants blinded to the bowel preparation. An adequate bowel preparation will be given a BBPS score of ≥ 6 . The secondary outcomes will also be assessed on the day of the procedure. Before colonoscopy patients will be asked to complete a questionnaire to assess their tolerability, hunger score and satisfaction with the dietary regimen. A subgroup analysis to assess the efficacy of bowel preparation on special population will also be conducted.

Study Process

Study Population

Inclusion Criteria:

 All adults≥18 years of age scheduled for colonoscopy at VMMC and willing to sign informed consent were eligible for ourstudy

Exclusion Criteria:

- 1. Patients with bowel obstruction and/or bowel perforation
- 2. Presence of a colostomy and/or history of a partial colon resection
- 3. Active gastrointestinal bleeding
- 4. Pregnancy
- 5. Inflammatory bowel disease
- 6. Diverticulitis

Sample Size:

At 95% confidence interval and 80% power of test, the minimum required sample size is 75 patients per group. This is also based on the previous proportion of adequate bowel preparation of 91% among low residue diet while 76% for clear liquid diet.

Statistical Analysis:

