From a patient standpoint, bowel preparation remains the biggest deterrent to an elective colonoscopy examination. Bowel preparations are generally poorly tolerated, which results in an important impediment to colorectal cancer screening and surveillance. Tolerability, often measured in clinical trials with "willingness to retake the preparation" or with respect to taste of the purgative solution, involves other factors that may lead to negative patient assessment. These include various dietary modifications or restrictions and important adjustments in work or social schedule that may affect the pre-procedural quality of life and directly influence adherence.

Overall, patient's tolerability and satisfaction were better in the LRD group than the CLD group. The present study showed that the proportion of patients having abdominal pain/cramping/discomfort and bloatedness are significantly lower in LRD group compared to CLD group. In addition, the proportion of patients in the LRD group was less hungry before colonoscopy as compared to CLD group. Our study also showed a higher proportion of patients in the LRD group rated the procedure easy and fair compared to CLD group. These results were parallel to other studies.

However, in our subgroup analysis, no difference was found among diabetics, chronic kidney disease and chronic liver disease patients when the two groups were compared with regards to patient's tolerability and satisfaction.

The present study has some limitations. It is a single-center study with arelatively small sample size. In addition, another limitation of the study is the sample size included in the chronic kidney disease(total of 17) and chronic liver disease(10) were small compared to elderly population(116) and diabetics(61),hence we cannot totally assessed their impact on the adequacy of bowel preparation.

Conclusion

Patients on a low residue diet for bowel preparation achieved an adequate bowel preparation that is non-inferior to patients on a clear liquid diet. Furthermore, the study showed that patients tolerability and overall satisfaction were better on the low residue diet group. Patients

in the LRD group would be more willing to repeat the same bowel regimen as compared to CLD group. However, the study also showed no statistical significance on patient's tolerability and satisfaction among diabetics, chronic kidney disease and chronic liver disease patients.

REFERENCES:

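### Tolerability outcomes are all tested at an unadjusted 5%, yet the Conclusion and the elderly Results are worded as established superiority; willingness to repeat and the elderly findings are the least secure

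*Protocol*

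**What the plan says.** The protocol's Statistical Analysis section names the tests ("t-test will be used to compare means such as BBPSscore, while chi square test will be utilized for categorical variables") and one significance level ("All significant test will be done at 5 % level"). It gives no adjustment.

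The Outcomes section makes adequacy on the Boston scale primary and tolerability secondary: "Secondary outcomes such as patient's tolerability of the regimen will be assessed by inquiring on the occurrence of gastrointestinal symptoms". It adds that before the procedure "patients will be asked to complete a questionnaire to assess their tolerability, hunger score and satisfaction with the dietary regimen". Nothing ranks the secondary outcomes among themselves or calls any of them exploratory. On subgroups, the same section says only that "A subgroup analysis to assess the efficacy of bowel preparation on special population will also be conducted", while the specific objective concerns tolerability in the special populations.

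The same document reports results. Table 3a tests nausea/vomiting, abdominal pain, bloatedness, hunger, satisfaction and willingness to repeat. Tables 3b to 3e repeat the six in diabetes, chronic kidney disease, chronic liver disease and the elderly. Unadjusted p-values below 0.05 are starred.

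The Conclusion then states: "Furthermore, the study showed that patients tolerability and overall satisfaction were better on the low residue diet group", and that patients "in the LRD group would be more willing to repeat the same bowel regimen as compared to CLD group". For older patients the Results say "elderly patients who said yes is significantly higher for low residue diet group (93.5" (the bracketed figure is a percentage), against 81.5% on clear liquids, and report more abdominal pain on clear liquids with p=0.0343.

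**The concern.** Efficacy is claimed only as non-inferior, so the tolerability findings are the trial's only superiority claims and its reason for preferring the low residue diet. When six outcomes each get the full 5%, the chance that at least one is falsely positive is well above 5%, and testing four subgroups adds to it. Three of the five starred overall p-values lie between 0.0178 and 0.0277, and the three starred elderly values between 0.0343 and 0.0475. Values of this size can lose significance under a modest correction. A reader would take the Conclusion as confirmed on every item when the protocol made no provision for confirming several at once.

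**Working it through.** **1. Reproduce the printed p-values.** Inputs are the Table 3a counts (75 per arm, low residue v clear liquid). The tests are Pearson chi-square without continuity correction, and a two-sample t-test for hunger.

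| Outcome | Data | Recomputed p | Printed p |
|---|---|---|---|
| Nausea/vomiting | 4 v 9 | 0.1468 | 0.1481 |
| Abdominal pain | 12 v 26 | 0.0086 | 0.0088 |
| Bloatedness | 20 v 33 | 0.0264 | 0.0269 |
| Hunger | 4.16 (SD 0.81) v 3.72 (SD 0.95) | 0.0027 | 0.0027 |
| Satisfaction (easy/fair/difficult) | 9/59/7 v 3/54/18 | 0.0178 | 0.0178 |
| Willingness | 70 v 61 | 0.0271 | 0.0277 |

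The differences change no conclusion. The printed values are used from here.

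**2. Chance of at least one false positive in six tests.** If independent: 1 − 0.95^6 = 0.265. The outcomes are correlated, so equal correlation was assumed and simulated with a normal model: 21% at 0.5 and 14% at 0.8.

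**3. Adjust the six overall p-values.** Holm multiplies the ordered p-values by 6, 5, 4, 3, 2, 1 and keeps the running maximum:
- hunger 6 × 0.0027 = 0.0162
- abdominal pain 5 × 0.0088 = 0.0440
- satisfaction 4 × 0.0178 = 0.0712
- bloatedness 3 × 0.0269 = 0.0807
- willingness 2 × 0.0277 = 0.0554, raised to 0.0807
- nausea/vomiting 0.1481

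Hochberg uses the same products but takes the running minimum from the largest p downwards. Bonferroni multiplies each p by 6. Benjamini-Hochberg multiplies by 6/rank, with the running minimum from the top (willingness: 6/5 × 0.0277 = 0.0332).

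| Outcome | Bonferroni | Holm | Hochberg | Hommel | Benjamini-Hochberg |
|---|---|---|---|---|---|
| Hunger | 0.0162 | 0.0162 | 0.0162 | 0.0162 | 0.0162 |
| Abdominal pain | 0.0528 | 0.0440 | 0.0440 | 0.0352 | 0.0264 |
| Satisfaction | 0.1068 | 0.0712 | 0.0554 | 0.0415 | 0.0332 |
| Bloatedness | 0.1614 | 0.0807 | 0.0554 | 0.0538 | 0.0332 |
| Willingness | 0.1662 | 0.0807 | 0.0554 | 0.0554 | 0.0332 |
| Nausea/vomiting | 0.8886 | 0.1481 | 0.1481 | 0.1481 | 0.1481 |

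The last column controls the false discovery rate, not the family-wise rate.

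**4. Change the family.**
- Table 5 adds one distinct item, completing the preparation (p=0.4062). With seven tests, Holm gives hunger 7 × 0.0027 = 0.0189 and abdominal pain 6 × 0.0088 = 0.0528.
- With only hunger, satisfaction and willingness as a questionnaire family, Holm gives satisfaction 2 × 0.0178 = 0.0356. Willingness is 0.0277, raised to 0.0356. Both pass.
- With all 30 tests of Tables 3a to 3e, the smallest adjusted p is 30 × 0.0027 = 0.081. Nothing passes.

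**5. Elderly subgroup (Table 3e).** The printed p-values are 0.0343, 0.0345, 0.0475, 0.0832, 0.0845 and 0.0845. Holm gives 6 × 0.0343 = 0.2058 for the three starred results. Hochberg, Hommel and Benjamini-Hochberg all give 0.0845. One caveat: clear-liquid abdominal pain is printed as 34 (37.0) of 54, but 37.0% corresponds to 20/54. A count of 20 gives p=0.0336, close to the printed 0.0343, so the printed p is taken as the working value.

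**The case against.** **Survival depends on choices that the protocol does not make.** A reader might infer that satisfaction and willingness fail multiplicity control outright. The documents do not support that. Satisfaction passes Hommel, both pass Benjamini-Hochberg, and both pass Holm in a three-item questionnaire family, a grouping that the Outcomes text makes arguable. Equally, a list saying that only hunger and abdominal pain survive is not secure, because abdominal pain fails Bonferroni over six and Holm over seven. This objection stands and limits the point.

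**There is a hierarchy.** Primary and secondary outcomes are separated. What is absent is an order within the secondary outcomes.

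**The pattern as a whole favours the low residue diet.** Five of six overall p-values are below 0.05, all in one direction. Under a global null with assumed equal correlation, this happens in about 0.25% of draws at 0.5 and 1.5% at 0.8. An ordinal test of satisfaction, which is not the planned test, gives p=0.0047. This supports a general tolerability advantage, but it does not confirm each named item.

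**The 30-test error rate is a poor headline.** Independence would give 1 − 0.95^30 = 79%, but the subgroups overlap with each other and with the whole (116 of 150 patients are elderly). The Conclusion claims no tolerability benefit in diabetes, kidney or liver disease, so 18 of the 30 tests support no positive claim. It makes no separate claim for the elderly either; those claims stand in the Results.

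**A statistical analysis plan might hold the multiplicity rule.** That would answer a complaint about missing detail. Here the protocol states the flat 5% rule, applies it and draws conclusions from it in the same document.

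**Conclusion.** The point holds in limited form: an unadjusted 5% rule is followed by claims worded more firmly than it can carry. The chance of at least one false positive among the six overall tests is about 14% to 26%, on an assumed equal correlation of 0.8 to 0.

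- **Willingness to repeat**, which has its own sentence in the Conclusion, fails every family-wise method tried on the six outcomes.
- **Elderly results**: none survives any method tried within that subgroup, given the printed p-values.
- **Satisfaction and bloatedness** fail Bonferroni, Holm and Hochberg on the six; satisfaction passes Hommel, and both pass false discovery rate control.
- **Abdominal pain** is borderline across families.
- **Hunger** is the most robust, failing only when all 30 tests are pooled.

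It would go too far to infer that the tolerability advantage is spurious. The overall direction is consistent, and the primary outcome is untouched. That the answer for satisfaction changes with family and method is the reason to call these results nominal.

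**What to change.** In the Statistical Analysis section, state that p-values for secondary outcomes and subgroups are unadjusted and exploratory, and report each difference with its 95% CI. For willingness, for example, this is 93.3% − 81.3% = 12.0 points, with standard error √(0.933 × 0.067/75 + 0.813 × 0.187/75) = 0.053 and a CI of about 1.5 to 22.5 points.

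In the Results and Conclusion, replace *showed* and *significantly* for satisfaction, bloatedness and willingness with wording such as *nominally better, unadjusted*. Remove the significance wording for the elderly.

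Holm or Hochberg results may be added only as a sensitivity analysis clearly labelled post hoc, with the family stated. They should not be written in as a planned rule: the p-values are already known, so a family and method chosen now would not control error.

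The cost is one sentence in the methods, intervals from data already tabulated, and edited claims. The downside is that the satisfaction, bloatedness, willingness and elderly findings become nominal only.
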